2.5.3 Handling of missing values/censoring/discontinuations

The repeated measure ANCOVA modeling as described in the previous section is based on a direct likelihood method with an assumption of missing at random for the missing data mechanism. That means, missing data, including those from dropouts, will be implicitly predicted based on similar patients. By similar we mean patients with similar baseline covariates, measurement histories and who were randomized to the same treatment arm. Various analyses to assess the sensitivity of the primary analysis results to the MAR assumption are described in [section 2.5.5](#).

Data collected more than three months after patients permanent discontinuation of the study medication will be excluded from analyses in both the Safety and PPS analyses. In addition, data collected after patients starting treatments for AD or cognitive impairment will be excluded from “on-treatment” analyses.

Patients with no post-baseline assessments available will be excluded from the primary analysis. However, these patients will contribute to the imputation model for the missing GCCS scores in the sensitivity analyses.

Table 2-3 Overview of missing data handling in analyses for primary endpoint

Analysis	Analysis Set	Data excluded	Missingness assumption	Analysis method	Time points included	Imputed dataset required?
Estimand: The treatment effect had all patients stayed ‘on-treatment’ for the 3-year planned follow-up duration (Under ‘as-treated’ principle)						
Primary	SAF	Off-treatment (>3 months after last dose) After start of treatment for AD or cognitive impairment	MAR	Repeated measure ANCOVA	Weeks 26, 52, 78, 104, 130 and Week 156	No
Sensitivity to Primary analysis	SAF	Off-treatment (>3 months after last dose) After start of treatment for AD or cognitive impairment	MNAR for missing data due to death, HF hosp., stroke	Tipping point analysis followed by ANCOVA	Baseline, Weeks 26, 52, 78, 104, 130 and Week 156	Yes

	SAF	Off-treatment (>3 months after last dose) After start of treatment for AD or cognitive impairment	MNAR for missing data after starting treatments for AD or cognitive impairment	Tipping point analysis followed by ANCOVA	Baseline, Weeks 26, 52, 78, 104, 130 and Week 156	Yes
	SAF	Off-treatment (>3 months after last dose) After start of treatment for AD or cognitive impairment	MNAR for missing values due to withdrawal for unknown reasons	Tipping point analysis followed by ANCOVA	Baseline, Weeks 26, 52, 78, 104, 130 and Week 156	Yes
	SAF	Off-treatment (>3 months after last dose) After start of treatment for AD or cognitive impairment	MNAR for missing data after starting treatments for AD or cognitive impairment	Jointly model longitudinal measurements and time to starting treatments for AD or cognitive impairment	Baseline, Weeks 26, 52, 78, 104, 130 and Week 156	No
Estimand: The treatment effect had all patients completed the planned follow-up of 3 years regardless of premature study drug discontinuation (under 'Intention-To-Treat' principle)						
Supportive	FAS	No	MAR	Repeated measure ANCOVA	Weeks 26, 52, 78, 104, 130 and Week 156	No
Sensitivity to supportive analysis	FAS	No	MNAR due to death, HF hosp., stroke	Tipping point analysis followed by ANCOVA	Baseline, Weeks 26, 52, 78, 104, 130 and Week 156	Yes
	FAS	No	MNAR after starting treatments for AD or cognitive impairment	Tipping point analysis followed by ANCOVA	Baseline, Weeks 26, 52, 78, 104, 130 and Week 156	Yes
Estimand: The treatment effect had all patients completed the study treatment as per protocol schedule without major protocol deviations (under 'as treated' principle)						
Supportive	PPS	Off-treatment (>3 months after last dose) After start of treatment for AD or cognitive impairment	MAR	Repeated measure ANCOVA	Weeks 26, 52, 78, 104, 130 and Week 156	No
	PPS2	Off-treatment (>3 months after last dose) After start of treatment for AD or cognitive impairment	MAR	Repeated measure ANCOVA	Weeks 26, 52, 78, 104, 130 and Week 156	No
Estimand: Measure of treatment effect of interest MAR = Missing At Random; MNAR = Missing Not At Random; MI = Multiple Imputation						

Following sections provide more detail on the specifications for supportive and sensitivity analyses on primary endpoint as outlined above.

2.5.4 Supportive analyses

In addition to the planned primary analysis in [Section 2.5.2](#), the same repeated measure ANCOVA will be performed in the following three analysis sets as supportive analyses as described in [Table 2-3](#):

- **Targeting treatment effect had all patients completed planned follow up of 3 years regardless of early study drug discontinuation**
Based on FAS, including all available data (even after treatment discontinuation and after start of treatments for AD or cognitive impairment)
- **Targeting treatment effect had all patients completed the study treatment as per protocol schedule without major protocol deviations**
Based on the per-protocol set, including ‘on-treatment’ data collected prior to the start of treatments for AD or cognitive impairment only.
- **Targeting treatment effect had all patients completed the study treatment as per protocol schedule without major protocol deviations and study treatment exposure and compliance defined in PPS2**
Based on the per-protocol set 2 (PPS2), including ‘on-treatment’ data collected prior to the start of treatments for AD or cognitive impairment only.

Summaries of absolute values and change from baseline in the GCCS and domain-specific composite z-scores by treatment group and visit will be presented. Figures will be produced to visually show both the raw and the model-based mean global composite z-scores and mean domain-specific composite z-scores by visit over study period for each treatment group. These will be done in both the Safety and FAS with the same data inclusion rules as for the above repeated measure ANCOVA modeling in the Safety and FAS.

Analysis of primary endpoint will also be performed based on pre-defined subgroups as in [Section 2.2.1](#) on the Safety set including ‘on-treatment’ data collected prior to the start of treatments for AD or cognitive impairment. The analysis will be done using a similar repeated ANCOVA model as for the primary analysis at individual subgroup level separately, while the p-values of the subgroup-by-treatment interaction will be derived from a similar model but with additional terms including the subgroup, the interaction term of subgroup-by-treatment.

2.5.5 Sensitivity analysis

The primary analysis methods are consistent under the assumption of ‘missing at random (MAR)’ for the missingness mechanism. Though this is deemed to be an appropriate choice for the primary analysis, this is an untestable assumption based on the observed data ([CHMP, 2010](#), [National Research Council, 2010](#)). Indeed it is conceivable that censoring, respectively the missing data mechanism (e.g., due to death) may be informative and that the cognitive function decline in patients who died would have been steeper than estimated under the MAR assumption. Thus, the primary analysis would favor the valsartan group in the presence of a reduction in mortality in the LCZ696 group. Alternatively, patients starting medications for treatment of AD or cognitive impairment may have had a steeper decline than estimated under the MAR assumption, if they would have not started the medication.

Due to this uncertainty on the missingness mechanism, the following sensitivity analyses will be performed to investigate the sensitivity of the primary analysis results to the MAR assumption.

Tipping point analysis

First, a tipping point analysis ([Permutt 2016](#)), which falls into the class of pattern mixture models, will be performed to evaluate the MAR assumption for missing data due to death, HF hospitalization and stroke.

This sensitivity analysis assumes that missing data due to death, HF hospitalization and stroke are missing not at random (MNAR). More specifically, it assumes that missing GCCS values due to death, HF hospitalization and stroke could have been worse than those imputed under the MAR assumption. It is implemented in the following steps:

1. Multiple (e.g. 100) imputations of missing GCCS values under a MAR assumption are generated, resulting in multiple (100) complete data sets. This imputation is based on predicted GCCS values from the fitted repeated measures ANCOVA model for the GCCS values (at baseline, Weeks 26, 52, 78, 104, 130 and Week 156) with treatment, age group (<75, ≥75 years), baseline MMSE status (<28, ≥28), baseline cerebrovascular disease burden, visit and treatment-by-visit interaction as factors having fixed effects assuming a common unstructured covariance matrix among visits between treatment group. SAS proc MI FCS statement is used to impute missing values in the following sequence: factor variables in the increasing order of missing frequency, the GCCS at baseline, Weeks 26, 52, 78, 104, 130 and Week 156.
2. For each completed data set, the imputed GCCS values at a given visit for patients who died, or had a HF hospitalization or stroke since the preceding visit, a penalty factor would be applied to the imputed values to reflect that the MAR approach may have overestimated the missing values, e.g. by assuming the actual GCCS values could be a certain percentage (e.g. 5%) worse than MAR based imputations for discontinuations due to death, HF hospitalization and stroke. If the MAR-imputed GCCS value is positive, the final value will be 95% x the imputed value; if the MAR-imputed GCCS value is negative, the final value will be 105% x the imputed value.
3. The primary analysis model as described above will be fitted to the 100 completed data sets following the application of the penalty factor in step 2 which produces 100 sets of parameter estimates and associated covariance matrices.
4. These 100 sets of parameter estimates are then combined by using Rubin's rules to derive overall estimates and their confidence intervals. In a similar manner to the primary analysis, a standardized effect size estimate (Cohen's d) and 95% CI will also be reported using the pooled SD.

The analysis will be repeated for varying penalty factors in a range between 0 and 50%. It is performed using 'on-treatment' data in the SAF, as done in the primary analysis. Tipping point analyses will be performed separately to assess the sensitivity of the results to MAR assumptions under the following situations:

- for missing data due to censoring at the start of AD and cognitive impairment treatments, including on-treatment data only in the SAF
- for missing data due to withdrawal for unknown reasons, including on-treatment data only in the SAF
- for missing data due to censoring at the start of AD and cognitive impairment treatments, including all data in the FAS
- for missing data due to withdrawal for unknown reasons, including all data in the FAS

In a similar procedure, missing values due to respective reasons will be imputed assuming MNAR while assuming all other missingness mechanism to be MAR.

If model convergence issue arises in the tipping point analysis, the model in step 1 above will be modified by replacing the common unstructured covariance matrix with a compound symmetry covariance matrix between treatment groups. If convergence issue remains after implementing the compound symmetry covariance matrix, the model will be simplified by removing baseline cerebrovascular disease burden as explanatory factor from the model.

Joint model approach

To adjust for the non-ignorable missingness in the primary endpoint due to starting AD/CI related medication, a joint modeling of the primary longitudinal process and missingness mechanism will be performed using a shared parameter approach (Vonesh et al 2006). Specifically, a generalized linear mixed model (GLMM) for the longitudinal GCCS outcome and a Cox proportional hazard model for the time to starting AD/CI related medication will be fitted which share common unobserved patient-specific random effect. It is assumed that the longitudinal outcome process is independent of the time to starting AD/CI related medication conditional on the random effects.

Model for longitudinal outcomes

The repeated GCCS outcomes will be analyzed following a repeated measures ANCOVA model with treatment, age stratification factor, MMSE stratification factor, education level, baseline cerebrovascular disease burden, APOE4 status (carrier vs. non-carrier) are included as factors and baseline GCCS, assessment time (in days), assessment time by baseline GCCS and assessment time by treatment interaction as covariates having fixed effects. Further, a patient-specific random intercept and random slope (on time) is fitted to the model. In general, the model has the following mathematical form:

$$y_i(t) = m_i(t) + e_i(t)$$
$$m_i(t) = X_i^T(t)\beta + (b_{0i} + b_{1i}t)$$

where

$y_i(t)$ =GCCS outcome for i-th patient at time t (assessment time in months)

$m_i(t)$ = 'True' (unobserved) patient-specific mean GCCS outcome for i-th patient at time t

$X_i(t)$ = Covariate vector having fixed effects on mean GCCS outcome for i-th patient (treatment, age stratification factor, MMSE stratification factor, education level, baseline

cerebrovascular disease burden, APOE4 status, baseline GCCS, assessment time, assessment time by baseline GCCS and assessment time by treatment)

β = Parameter vector representing fixed effects of covariate vector $X_i(t)$ on mean GCCS outcome at time t

b_{0i} =Patient-specific random intercept

b_{1i} =Patient-specific random slope on time

$e_i(t)$ = Measurement error,

Assumption:

- (b_{0i}, b_{1i}) 's are assumed to be following bivariate normal distribution with mean vector 0 and unstructured covariance matrix independently for all patients
- $e_i(t)$'s are assumed to be independently normally distributed with mean vector 0 and an covariance matrix with no correlation between the time points and an common variance σ_e^2 on the diagonal elements

Model for time to starting AD or CI related medication

Time to starting AD or CI related medication from randomization will be calculated as –

- Date of starting AD or CI related medication – Randomization date +1

Patients who do not start AD or CI related medication, their data will be censored at the earlier of –

- Last known date patient took study medication
- Date of withdrawal of consent
- Date of last visit

A exponential regression is fitted to the time to starting AD or CI related medication.

$$\lambda_i(t|H_i(t), X_i) = \lambda_0 \exp(X_i^T \gamma + \alpha m_i(t))$$

where

$\lambda_i(t|H_i(t), X_i)$ =Conditional intensity function at time t for i-th patient given the covariate and history of outcomes until time t, $H_i(t)$

λ_0 =Baseline hazard function that is constant over time

γ = Parameter vector representing fixed effects of time-independent covariate vector X_i on event risk (hazard) at time t

α =Fixed effect of ‘true’ patient-specific mean outcome at time t

A constant function will be assumed for the baseline intensity function. over time. Assuming that the longitudinal GCCS outcome process and event process of starting AD or CI related medication are independent conditional on the random effects, the conditional likelihood is computed as multiplication of the likelihood from GCCS outcome process and event process. Parameter estimation will be done through numerically maximizing the marginal likelihood obtained from numerically integrating the conditional likelihood over the distribution of random effects.

Of note, the modeling may fail to converge yielding unreliable or no estimate for parameters if the incidence of start of AD/CI related medication are low. In such a case, restrictions may be imposed on the form of baseline intensity function to change to a parametric baseline intensity (e.g. Weibull function) which will be documented in the clinical study report section 9.7. If the model still fails to converge, the results may be excluded from the clinical study report.

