#### 3.1 Study design

This study is a multi-center, randomized, double-blind, parallel group, active comparator trial designed to evaluate the overall effect of LCZ696 compared to valsartan on cognitive function as assessed by a comprehensive cognitive battery in patients with HFpEF (Figure 3-1). The study population will consist of patients  $\geq 60$  years of age with chronic symptomatic HF (NYHA class II-IV) and a left ventricular ejection fraction (LVEF)  $>40\%$ . Patients will be randomized in a 1:1 fashion to either LCZ696 200 mg bid or valsartan 160 mg bid.

Cognitive function will be assessed at baseline and every six months up to 3 years by a comprehensive cognitive battery, and MMSE will be assessed annually. Patients scoring  $<24$  on the MMSE scale during screening will be excluded from the study. Patients will be stratified based on age ( $< 75, \geq 75$  years), MMSE score ( $< 28, \geq 28$ ), and if participating in the PET imaging substudy, amyloid status (amyloid positive/negative). APOE4 is a strong predictor of cognitive impairment (Lim et al 2015) and A $\beta$  accumulation. Therefore, patients will be genotyped for APOE4 allele status.

[figure not shown]
The study will also evaluate the impact of LCZ696 therapy compared to valsartan on  $\beta$ -amyloid deposition in the brain using florbetapir  $^{18}\text{F}$  PET imaging in a subset of patients. PET imaging requires specialist centers experienced in the technique that are in close proximity to a radiopharmaceutical production facility, thus a subset of centers will be selected as PET centers. To ensure high quality of imaging data, PET imaging will be conducted in all eligible patients at selected PET capable centers. Amyloid PET imaging will be performed at randomization, at 18 months, and at 3 years (EOS Visit). If a patient permanently discontinues treatment prior to 3 years, a PET scan should be done at the end of treatment visit (EOT visit) if a prior scan was performed more than twelve months ago. End of study (EOS) scan will not be required if EOT scan is performed within 12 months of end of study visit. All PET scans will be evaluated centrally.

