2.5.2 Statistical hypothesis, model, and method of analysis

The change from baseline in the GCCS of CogState test battery will be analyzed using a repeated measures analysis of covariance (ANCOVA) model in which treatment, age stratification factor, MMSE stratification factor, education level, APOE4 status (carrier vs. non-carrier), baseline cerebrovascular disease burden, visit (Weeks 26, 52, 78, 104, 130 and Week 156) and treatment-by-visit interaction are included as fixed-effect factors and baseline GCCS and visit-by-baseline GCCS interaction as covariates, with a common unstructured covariance matrix among visits between treatment groups. The adjusted mean changes at 3 years (Week 156) within each treatment, the difference in mean changes at 3 years (Week 156) between the two treatments, and its 95% confidence interval obtained from the above model will be presented. In addition, the treatment difference (LCZ696-valsartan) in mean changes from baseline to 3 years will also be expressed based on a standardized effect size (Cohen's d) with a 2-sided 95% confidence interval. The Cohen's d will be estimated by using the adjusted between-treatment mean difference, divided by the estimated pooled standard deviation. The estimated standard deviation for the mean difference is:

$$SD = \left(\frac{1}{n_1} + \frac{1}{n_2} \right)^{1/2} \hat{\sigma}$$

where n1 and n2 are the number of patients within each treatment group and $\hat{\sigma}$ is the pooled standard deviation of the within treatment group adjusted mean change. Cohen's d can be rewritten in terms of t value of the estimated between treatment group difference based on the adjusted mean changes from the model mentioned above:

$$t = \frac{\hat{\mu}_1 - \hat{\mu}_2}{SD} = \frac{\hat{\mu}_1 - \hat{\mu}_2}{\left(\frac{1}{n_1} + \frac{1}{n_2} \right)^{1/2} \hat{\sigma}}$$

$$\hat{d} = \frac{\hat{\mu}_1 - \hat{\mu}_2}{\hat{\sigma}} = \left(\frac{1}{n_1} + \frac{1}{n_2} \right)^{1/2} \times t$$

Confidence interval (CI) of Cohen's d is based on 95% CI of the noncentrality parameter of t value divided by the square root of the degrees of freedom from the estimated between treatment group adjusted mean change (Cumming and Finch 2001). The analysis is based on a direct likelihood method with an assumption of missing at random (MAR) for the missing data mechanism.

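### The GCCS tipping-point imputation model omits education level and APOE4 status, although the model fitted to the imputed data includes both

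*SAP*

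**What the plan says.** The primary repeated-measures ANCOVA (SAP 2.5.2) adjusts for treatment, age stratum and "MMSE stratification factor, education level, APOE4 status (carrier vs. non-carrier), baseline cerebrovascular disease burden", plus visit, treatment-by-visit, baseline GCCS and visit-by-baseline GCCS. SAP 2.5.3 explains what MAR means for that model: "By similar we mean patients with similar baseline covariates, measurement histories and who were randomized to the same treatment arm".

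The tipping-point analysis is in SAP 2.5.5. Step 1 imputes under MAR from a model "with treatment, age group (<75, ≥75 years), baseline MMSE status (<28, ≥28), baseline cerebrovascular disease burden, visit and treatment-by-visit interaction as factors". PROC MI with the FCS statement fills in "factor variables in the increasing order of missing frequency, the GCCS at baseline, Weeks 26, 52, 78, 104, 130 and Week 156". Step 2 applies a penalty to the imputed values. In step 3, "The primary analysis model as described above will be fitted to the 100 completed data sets". On the penalty, the SAP says: "The analysis will be repeated for varying penalty factors in a range between 0 and 50" per cent.

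The joint model in the same section keeps both education level and APOE4 status. On the second of these, Protocol 3.1 states: "APOE4 is a strong predictor of cognitive impairment". The SAP gives no reason for leaving the two covariates out of step 1, and SAP section 4 lists no changes to the protocol analyses.

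**The concern.** A tipping-point series should vary one thing, the departure from MAR, and its zero-penalty end should be an MAR analysis comparable with the primary one. Here the imputation conditions on a smaller covariate set than the primary model. If dropout depends on education or APOE4 status, the primary MAR assumption can hold while the imputation's fails. Movement away from the primary estimate would then mix a change of imputation model with the penalty.

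The imputation is also uncongenial with step 3. Imputed values carry no direct effect of two covariates that the analysis model then estimates, so those effects are diluted. This matters most for patients with little or no post-baseline GCCS history, and in the run for data censored at the start of treatment for AD or cognitive impairment, where APOE4 carriers may plausibly be over-represented.

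**Working it through.** The plan states no figure on this point. The check is a comparison of the two models, followed by illustrations of size.

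**1. The yardstick.** SAP 3.1 plans 180 patients per group around d = 0.3. The normal approximation gives 2 × (1.960 + 0.842)² / 0.3² = 174.4, so 175 per group. Power at 180 is 81.2% (81.0% by noncentral t). The planned figure reproduces, and 0.3 is used as the benchmark below. With 180 per group, the standard error of d near zero is about √(2/180) = 0.105.

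**2. Covariates side by side.**

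| Term | Primary model and step 3 | Step 1 imputation |
|---|---|---|
| Treatment, visit, treatment-by-visit | yes | yes |
| Age group, MMSE status | yes | yes |
| Cerebrovascular disease burden | yes | yes |
| Baseline GCCS | covariate, with visit interaction | yes, in the set of GCCS variables |
| Education level | yes | no |
| APOE4 status | yes | no |

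The gap is exactly education level and APOE4 status. Baseline GCCS is not a real omission.

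**3. Hand illustration, APOE4 only (all inputs assumed).** Carriers are 25%. In one arm 30% are missing regardless of APOE4. In the other, 50% of carriers and 25% of non-carriers are missing.
- Missing share in the second arm: 0.25 × 0.50 + 0.75 × 0.25 = 0.3125
- Carriers among the missing: 0.125 / 0.3125 = 0.40
- Carriers among the observed: 0.125 / 0.6875 = 0.182
- Shift in the arm difference: 0.3125 × (0.40 − 0.182) × β = 0.068β, where β is the carrier effect left after conditioning on earlier scores
- For β of 0.15 to 0.30 SD: 0.010 to 0.020 SD, or 3% to 7% of 0.3

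**4. Simulation (all effects assumed).** There were 520 patients, 25% carriers, 40% with low education, about 33% missing at Week 156, true d = 0 and zero penalty. GCCS was imputed visit by visit from each patient's own earlier scores, with and without the two covariates. It was then analysed by ANCOVA at the last visit with both. There were 150 replicates per row.

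| Dropout depends on the covariates | APOE4 / education effect on 3-year change | Mean shift in d from omitting both (simulation SE) | APOE4 coefficient: included → omitted |
|---|---|---|---|
| equally in both arms | 0.2 / 0.1 | −0.001 (0.002) | −0.211 → −0.151 |
| equally in both arms | 0.4 / 0.2 | +0.003 (0.003) | −0.417 → −0.299 |
| in one arm only | 0.2 / 0.1 | +0.043 (0.002) | −0.214 → −0.149 |
| in one arm only | 0.4 / 0.2 | +0.079 (0.003) | −0.411 → −0.285 |

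With both covariates in the imputation model, mean d agrees with the complete-data result to within 0.005 in every row. In the first row the APOE4 coefficient shrinks by (0.211 − 0.151) / 0.211 = 28%, and the education coefficient by (0.152 − 0.122) / 0.152 = 20%.

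The simulated shifts exceed the hand figure because two covariates act and the assumed effects are larger. The residual SD was about 0.024 / 0.047 = 0.51, so APOE4 effects of 0.2 and 0.4 are about 0.4 and 0.8 SD. The upper end is therefore a generous case.

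**The case against.** Several points against the concern are sound.

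- **History carries much of the information.** It is tempting to infer that imputed carriers are simply given the average patient's course. They are not, because imputation conditions on each patient's own GCCS scores. Suppose the carrier effect grows linearly to 0.30 SD at Week 156, with correlation 0.8 between adjacent visits (both assumed). For a patient last seen at Week 130, the part lost is 0.30 − 0.8 × 0.25 = 0.10 SD. More is lost for early dropouts.
- **A material shift needs arm-dependent dropout.** The documents give no carrier prevalence, covariate effect or APOE4-specific dropout. If the dependence is the same in both arms, the effects on d cancel. The diluted covariate coefficients are not themselves of interest.
- **The list may be shorthand.** Step 1 orders factor variables by how often they are missing, which could hint at a wider set. However, it names no factors beyond those listed, so this is grounds for clarifying the text and does not show that the two covariates are included.
- **Adding the covariates will not make the zero-penalty run equal the primary analysis.** Under SAP 2.5.3, patients with no post-baseline data are excluded from the primary analysis but enter the imputation. FCS regressions also allow covariate effects to vary by visit, which the primary model does only for baseline GCCS.
- **Other analyses are less exposed.** The joint model keeps both covariates, and the SUVr imputation model (SAP 2.7.1) includes APOE4.

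These points limit the importance of the omission. They do not explain why step 1 conditions on less than the model it feeds.

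**Conclusion.** The point holds as a minor defect in a sensitivity analysis. As written, the GCCS imputation is MAR given a smaller covariate set than the primary analysis and is uncongenial with step 3. Conditioning on less might look like assuming less. In general it assumes more, because missingness must then be ignorable without education and APOE4.

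The expected shift in d is about zero when dropout depends on the two covariates equally in both arms. When the dependence is confined to one arm, it is roughly 0.01 to 0.08, at most about a quarter of the benchmark (0.08 / 0.3 = 0.27) and less than one standard error (0.08 / 0.105 = 0.76). These sizes rest wholly on assumed effects and dropout patterns.

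A reader might infer that the primary result is biased or that the tipping-point series is invalid. The documents support neither. The primary estimate comes from the direct-likelihood model in SAP 2.5.2, which contains both covariates and uses no imputed data, and the main conclusion is drawn from it. The tipping-point series remains informative, but its starting point is not cleanly matched to the primary MAR assumption.

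**What to change.** Add education level and APOE4 status as main effects to the step 1 PROC MI FCS model, and to the other GCCS tipping-point runs (SAF and FAS) that follow the same procedure. Main effects are enough. Imputing within arm or adding covariate-by-treatment terms would depart from the primary model in a new way. If the two covariates were always meant to be among the factor variables, say so in step 1.

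Report the zero-penalty result beside the primary estimate, and state that some difference is expected because patients with no post-baseline data enter only the imputation.

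The cost is small. Both variables are already needed for step 3. The downside is two more terms in a model for which SAP 2.5.5 already foresees convergence problems, and any missing values of these covariates would have to be imputed as well.
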